1. Background and Rationale

1.1. Overview of Allogeneic hematopoietic cell transplantation (HCT) and Graft Versus Host Disease (GVHD) prevention

Allogeneic hematopoietic cell transplantation (HCT) is a potentially curative treatment modality for many patients with hematological malignancies, solid tumors and acquired or congenital non-malignant disorders. Despite recent advances in the understanding of transplantation immune tolerance, graft versus host disease (GVHD) remains a principal obstacle to achieve successful outcomes. Serious infections and impairment of generalized immune dysfunction are responsible for GVHD-associated mortality. GVHD incidence and severity depends primarily on donor and recipient matching for human leukocyte antigens (HLA) and the regimen used for post-grafting immune suppression. The NIH consensus development project working group recognized 2 main categories of GVHD, each with 2 subcategories. The acute GVHD (aGVHD) category is defined in the absence of diagnostic or distinctive features of chronic GVHD and includes (1) classic acute GVHD occurring within 100 days after transplantation and (2) persistent, recurrent, or late acute GVHD (features of acute GVHD occurring beyond 100 days, often during withdrawal of immune suppression). The broad category of chronic GVHD (c-GVHD) includes (1) classic chronic GVHD (without features or characteristics of acute GVHD) and (2) an overlap syndrome in which diagnostic or distinctive features of chronic GVHD and acute GVHD appear together.¹

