2.2. Secondary Objectives

- 2.2.1. Clinical objectives:
 - 2.2.1.1. Cumulative incidence of chronic GVHD
 - 2.2.1.2. Engraftment, relapse, non-relapse mortality, overall and relapse-free survival at one year.
- 2.2.2. Biological studies to test the pharmacodynamics of TAC/SIR/PANO combination for GVHD prevention:
 - 2.2.2.1. Immune Reconstitution determined by flow cytometry
 - 2.2.2.2. Histone acetylation of T cells and DC subsets by Western Blot and flow cytometry
 - 2.2.2.3. T reg immune-reconstitution, Foxp3+ expression and acetylation by flow cytometry
 - 2.2.2.4. Inflammatory cytokine and Biomarker expression profiling
 - 2.2.2.5. Stat-3 activation and acetylation
 - 2.2.2.6. Panobinostat pharmacokinetics

	Objective	Endpoint
Primary Clinical Objectives	Prospectively determine the cumulative incidence of acute GVHD grades 2-4 using TAC and SIR in addition to PANO for GVHD prevention. Study parameters: We will consider $\geq 43\%$ incidence of grade II-IV aGVHD not acceptable. We will use 23% incidence rate of GVHD as target.	GVHD severity stage and grading and distribution will be measured weekly from day of transplant to day 90 +/- 14 using standard scoring system. Stage of GVHD will be given for each site of involvement (e.g. skin, liver, and gut), as well as a composite score for overall acute GVHD grade. Pathologic confirmation of aGVHD will be dictated by usual clinical practice, and not

		mandated by this protocol. Treatment of GVHD will not be mandated.
Secondary Clinical Objectives	Cumulative incidence of chronic GVHD	GVHD with onset after 100 days post-HCT with presence of at least one diagnostic manifestation of chronic c-GVHD or distinct manifestation confirmed by biopsy or other relevant tests (eg PFT). Classified as: 1- Classic chronic GVHD - meets criteria for chronic GVHD and has no features consistent with aGVHD or 2- Overlap syndrome - features of acute and chronic GVHD exist together. C-GVHD will be measured prospectively in all patients on days 90+/-14 , 120 +/- 14, 150 +/- 14, 180+/- 14, 270+/- 30, and 365 +/- 30 as per standardized scoring system.
	Engraftment	Stable engraftment for WBC is defined as a sustained absolute neutrophil count > 500 over 3 days without cytokine support. Stable platelet engraftments is defined as count of > 20,000 over 7 days without transfusion support. Time to engraftment is defined as time from day 0 to day of sustained engraftment per above criteria for both platelets and WBC.

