- 3.3. **Sample Size and accrual rate.** It is estimated that 2 patients will be entered into the treatment study each month, therefore, we anticipate 24 months for completion of the study that will require **n=44** total patients for the treatment arm. We are planning to enroll **n=20** patients for “external control patients”. We anticipate 0.5 patients/month for “external control” subjects and accrual will happen concomitant to treatment arm patients. Therefore a total of **64** subjects will be accrued in total including treatment arm and external control.
- 3.4. **Patient Follow up.** Patients will be evaluated weekly from day of transplant until day 100 to measure acute GVHD using standard scoring system (defined in Appendix A). Stage of GVHD will be assessed for each site of involvement (e.g. skin, liver, and gut), as well as a composite score for overall acute GVHD grade determined. Pathologic confirmation of aGVHD will be dictated by usual clinical practice. Patient will be followed on days +90 +/-14, 120 +/- 14, 150 +/- 14, 180+/- 14, 270+/-30, and 360 +/- 30 for chronic-GVHD assessment and adverse events toxicity assessment. Taper of immunosuppression is suggested- not mandatory and treatment of GVHD is not mandated (section 6.2-6.3).
- 3.5. **Withdrawal.** from the study will take place under the following circumstances: those patients who sign consent for the study, but fail to initiate treatment due to:
- 3.5.1. denial of coverage from insurance provider
 - 3.5.2. disease progression prior to initiation of treatment
 - 3.5.3. death prior to initiation of treatment
 - 3.5.4. withdrawal of patient consent at any time after therapy

4. Patient Population: Inclusion and Exclusion criteria

- 4.1. **Inclusion Criteria:**
- 4.1.1. Male or female

- 4.1.2. Age \geq 18 years or older at time of enrollment
 - 4.1.3. Signed informed consent
 - 4.1.4. Hematologic disorder requiring allogeneic hematopoietic cell transplantation
 - 4.1.5. LVEF \geq 45% by MUGA scan or echocardiogram
 - 4.1.6. FEV1, FVC, and DLCO adjusted \geq 50% of predicted values on pulmonary function tests
 - 4.1.7. Transaminases (AST, ALT) $<$ 3 times upper limit of normal values
 - 4.1.8. Creatinine clearance calculated \geq 50mL/min
 - 4.1.9. Karnofsky Performance Status Score \geq 60%.
 - 4.1.10. HLA matched 8/8 (A, B, C, DRB1) related or unrelated donor
- 4.2. **Exclusion Criteria:**
- 4.2.1. Active infection not controlled with appropriate antimicrobial therapy

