- 10.12.1. GVHD: Date of onset of acute GVHD, names of immunosuppressive drugs received and dates, Date of onset of chronic GVHD, Organ staging will be assessed prior to therapeutic intervention, according to the consensus grading⁴⁴ (Appendix A). The diagnosis of Grades II-IV GVHD should be confirmed by histo-pathological examination whenever possible but is not mandatory. Pathology will be reviewed by H. Lee Moffitt Cancer Center pathologists.
 - 10.12.2. Study medications: Records of study medication used, dosages administered, and intervals between visits will be recorded during the study. Drug accountability will be noted by research pharmacy.
 - 10.12.3. AE: Significant findings made after the start of study drug which meet the definition of an AE and SAE must be recorded.
 - 10.12.4. Infections and relapse will be captured but they are not considered AE
- 10.13. Correlative studies.** See appendix F

11. Data and Safety monitoring:

The Data Safety & Monitoring Plan (DSMP) will ensure that this trial is well designed, responsibly managed, appropriately reported, and that it protects the rights and welfare of patients. The following internal and external review and monitoring processes provide oversight and active monitoring of this trial:

- The Principal Investigators (PI)
- The Scientific Review Committee (SRC)
- The Protocol Review and Monitoring Committee (PRMC);
- The Research Compliance Division (RCD) of the Cancer Center's Compliance Office;
- The Institutional Review Board.
- We will follow the Moffitt Cancer Center policy for monitoring of Investigator Initiated Trials (MRI-P.PSO.03)

The protocol includes a section that specifies the following with respect to Adverse Event (AE) reporting: what constitutes an AE (versus what is a serious adverse event), the entities to which AE should be reported, the timing of this reporting, and the person or persons responsible for reporting. This includes prompt (within one day of knowledge of the event) reporting to the IRB for unanticipated risks to subjects and reporting in writing within five working days to the IRB. It is required reporting of SAE to Novartis but not AEs as indicated in section 9. If necessary, corrective action and/or educational programs will occur to ensure subject safety and data integrity. Reports to the SRC, PMC, and IRB will be submitted as required.

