12.5 Analysis Plan for Secondary Endpoints

The demographic and clinical characteristics of subjects will be summarized using descriptive statistics; mean, median, standard deviation and range for continuous measures and counts and frequencies for categorical measures. Adverse events will be recorded, including the details of the duration and the severity. Time-to-event data such as overall survival (OS) and relapse-free survival (RFS) is measured from the date of transplantation. OS and RFS will be analyzed using the Kaplan-Meier method⁵¹. The cumulative incidence of relapse and non-relapse mortality will be computed by Gray method. Death and relapse will be considered as the competing risks of chronic GVHD and the cumulative incidence of chronic GVHD will be measured by Gray method. The association of time-to-event data with and without competing risks will be explored by the method by Fine and Gray⁵² and the Cox proportional hazards regression model⁵³, respectively.

For correlative studies (appendix F) results will be compared to an external control patient subset that will be treated with TAC/SIR with same inclusion and exclusion criteria as this protocol except that they will not be treated with PANO. For the regulatory T-cell repopulation, the profiles of regulatory T cell counts will be analyzed using generalized linear models for repeated measures based on generalized estimating equations. The comparisons of profiles of T-cells and DC cells with external control will be made using the Satterthwaite t-test.

The analysis of the secondary endpoints is considered exploratory and no multiplicity adjustment is planned for it. A two-sided p-value of <0.05 is considered statistically significant.

If we compare a total of 30 patients (**15 in treatment group and 15 in external control**) that will achieve 83% power to detect an effect size (mean difference divided by standard deviation) of 1.1 between two groups.

If we compare a total of 40 patients (20 in PANO group and 20 in external control) will achieve 87% power to detect an effect size (mean difference divided by standard deviation) of 1 between two groups.

13 Procedures and instructions

13.1 Publication of results: Any formal presentation or publication of data from this trial may be published after review and comment by Novartis and prior to any outside submission. Novartis must receive copies of any intended

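### The chronic GVHD endpoint counts only onset after day 100, while Appendix A sets no time limit, so early chronic or overlap cases have no place in the endpoint

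*Combined protocol and SAP*

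**What the plan says.** The objective and endpoint table in section 2.2 defines the chronic GVHD endpoint as "GVHD with onset after 100 days post-HCT with presence of at least one diagnostic manifestation", or a distinctive manifestation confirmed by biopsy or another test. It then sorts cases into classic chronic GVHD and a second class, "Overlap syndrome - features of acute and chronic GVHD exist together". The onset condition comes before the sorting and so governs both classes. The same cell sets the first scoring time: "C-GVHD will be measured prospectively in all patients on days 90+/-14". Section 3.4 gives the same first visit: "Patient will be followed on days +90 +/-14, 120 +/- 14, 150 +/- 14".

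Appendix A part 3 classifies GVHD by time and by features. Classic chronic GVHD and overlap syndrome carry no time limit. Day 100 serves only to divide classic from late-onset acute GVHD, and both acute classes require that chronic features be absent. Section 1.1 takes the same line: acute GVHD is "defined in the absence of diagnostic or distinctive features of chronic GVHD".

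Section 10.12.1 has the "Date of onset of chronic GVHD" recorded, with no time restriction. Under section 12.5, "the cumulative incidence of chronic GVHD will be measured by Gray method", with death and relapse as competing risks. That section also states: "The analysis of the secondary endpoints is considered exploratory".

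**The concern.** The protocol holds two definitions of chronic GVHD. The endpoint table uses a time cut plus features; Appendix A part 3 and section 1.1 use features. They disagree for any patient whose chronic features appear by day 100. Section 12.5 does not settle the matter: it sets no day-100 landmark and gives no rule for earlier onset.

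What is at stake is the first-listed secondary clinical objective. In a single-arm trial a cumulative incidence can be read only if it is clear what counts as a case. If the analyst follows the endpoint table, early cases drop out of the estimate. If the analyst follows Appendix A, they count. Leaving that choice until outcomes are known would make it post hoc.

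**Working it through.** The plan states no figure that depends on this definition, so there is none to reproduce. The check is a comparison of texts with two small pieces of arithmetic.

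**1. One patient through each definition.** Take a patient whose diagnostic chronic features first appear on day 85.

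- Section 2.2 endpoint: the features qualify, but day 85 is not after day 100. Not a chronic GVHD event.
- Appendix A part 3, chronic classes: no time limit applies. Classic chronic GVHD if acute features are absent, overlap syndrome if they are present.
- Appendix A part 3, classic acute GVHD: the time criterion is met (85 ≤ 100), but chronic features must be absent. Not classic acute.
- Section 1.1, acute GVHD: chronic features must be absent. Not acute.

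So the endpoint table excludes the patient on timing, and the acute definitions exclude the patient on features. Read literally, the case belongs to neither endpoint, although Appendix A calls it chronic.

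**2. Visit window.** Inputs: day 90 ± 14 and day 120 ± 14 (sections 2.2 and 3.4).

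- First chronic scoring window: 90 − 14 = 76 to 90 + 14 = 104, which is 104 − 76 + 1 = 29 days.
- Days in that window on or before day 100: 100 − 76 + 1 = 25 of 29.
- The next window opens at 120 − 14 = 106.

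Most permitted dates for the first chronic scoring visit therefore fall where a new finding cannot count under the endpoint table.

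**3. Size per case.** Inputs: 44 patients planned for the treatment arm (sections 3.3 and 12.1); everyone with at least one dose enters the secondary endpoints (section 12.3). Assume that all 44 are dosed, that no one is censored, and that an excluded early case stays in the denominator as a non-event. The estimate then equals events divided by patients, and k excluded cases lower it by k/44:

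- k = 1: 1/44 = 2.3 percentage points
- k = 2: 2/44 = 4.5 points
- k = 3: 3/44 = 6.8 points

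The values of k are illustrative; the documents give no rate of chronic or overlap GVHD by day 100. With censoring the figure per case is only approximate.

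**The case against.** The endpoint is exploratory and has no threshold, decision rule or sample size attached, so no go/no-go conclusion turns on it. The day-90 visit is weak evidence of error: it also serves the acute and toxicity assessments, and scoring shortly before an at-risk period opens is not in itself a flaw. The number of early cases may be small. In the earlier treatment study described in section 1.4, acute symptoms in the five overlap patients began between days 109 and 981, none by day 100. All of this stands and limits the weight of the point. It does not reconcile the two definitions.

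A reader might infer more than the documents support, in three ways:

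- **That the primary acute GVHD count is contaminated.** The organ-staging table in Appendix A part 1 does not ask about chronic features, so an early overlap case could be graded there as acute by oversight. But section 1.1 and Appendix A part 3 both exclude such cases from acute GVHD. Misfiling is a possibility, not a consequence of the plan, and the documents give no rate from which to compute an effect on the section 12.1 rule.
- **That the result will not be comparable with the 51% chronic GVHD quoted for the earlier tacrolimus/sirolimus arm.** That figure appears only in the background (section 1.1), no comparison with it is planned, and the documents do not say how that trial defined onset.
- **That early cases are lost from the data.** They are not. The onset date is recorded without a time limit (section 10.12.1), acute GVHD is assessed weekly to day 100 (section 3.4), and Appendix C lists organ assessments at days 28, 60 and 90. Such cases are left out of an endpoint definition and can be recovered.

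**Conclusion.** The inconsistency is real and limited. The endpoint table imposes a day-100 onset condition that Appendix A part 3 does not set for chronic GVHD and that section 1.1 does not support. Followed as written, it removes early chronic and overlap cases from the chronic GVHD cumulative incidence and gives them no place under acute GVHD. Any resulting bias is downward, about 2.3 points per case on a denominator of 44, under the assumptions shown. Its total cannot be estimated because the documents do not give the number of early cases. The conclusion rests on the contradiction between the texts; the day-90 window only supports it. The effect is confined to a secondary, exploratory estimate, and the data needed to correct it are already collected.

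**What to change.** - In the section 2.2 endpoint table, delete the condition that onset be after day 100. Define the endpoint as classic chronic GVHD or overlap syndrome under Appendix A part 3, at any onset time, dated by the onset recorded under section 10.12.1.
- State that the Appendix A part 3 rule applies when events on or before day 100 are classified: a case with chronic features is not classic acute GVHD. This makes an existing rule explicit. Because it bears on how events near the primary endpoint are sorted, it should be written down before outcomes are reviewed.

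The cost is a deleted phrase and one or two sentences. No visits, data items or patients are added, and the sample size is unchanged. There is one small downside. No dedicated chronic GVHD scoring is scheduled before the day-90 visit, so detection of onset before day 76 would rely on the weekly acute GVHD evaluations and the day 28 and day 60 organ assessments. The report should say so.

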12.1. Sample Size Determination

In our randomized Phase II trial of TAC and SIR vs. TAC and MTX as GVHD prophylaxis after allogeneic transplantation we observed an acute GVHD incidence of 43% (95% CI 30-63%) with TAC/SIR⁴. Simon's minimax two-stage design with 10% one-sided type I error and 10% type II error rate is used for study design as follows. We will consider 43% incidence of grade II-IV

acute GVHD (aGVHD) not warranting further study. We will use 23% incidence rate as a promising result to pursue further study. With these study parameters, 15 evaluable patients will be investigated in the first stage. If 7 or more of 15 evaluable patients experience the grade II-IV acute GVHD, the treatment will be stopped. Otherwise, once 9 or more of 15 patients completed the +90 (+/-14) days follow up without experiencing the grade II-IV acute GVHD 23 additional evaluable patients (a total of 38 evaluable patients) will be enrolled. If the number of patients experiencing the grade II-IV aGVHD is 12 or less, ($\leq 31.6\%$ incidence rate at day 100), the null hypothesis will be rejected and the regimen will be considered promising. An evaluable patient for primary endpoint is defined as patients who receive at least one dose of PANO per protocol and who neither relapse nor die of any reasons without experiencing grade II-IV aGVHD until day 100. A non-evaluable patient will be replaced and we anticipate a total of 44 patients will be accrued in order to account for 10% of competing risks (relapse or death without GVHD) at day 100.

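### Section 3.3's external-control rate (0.5 per month), accrual period (alongside a 24-month treatment arm) and target (20 controls, 64 subjects) do not agree: the rate and period give 12 controls and 56 subjects.

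*Combined protocol and SAP*

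**What the plan says.** All the accrual inputs stand in one paragraph, Section 3.3.

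- Treatment arm: "It is estimated that 2 patients will be entered into the treatment study each month", and "we anticipate 24 months for completion of the study that will require" 44 treated patients. Section 12.1 gives the same 44.
- Control target: "We are planning to enroll n=20 patients for “external control patients". Appendix F repeats the 20 and adds that these patients sign a consent form of their own.
- Control rate: "We anticipate 0.5 patients/month for “external control” subjects".
- Control timing: "accrual will happen concomitant to treatment arm patients".
- Total: 64, presented as following from the above.

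Section 12.5 gives two power statements for the correlative comparisons. One is for 15 vs 15 patients: 83% at effect size 1.1. The other is for "40 patients (20 in PANO group and 20 in external control) will achieve 87% power" at effect size 1.0. The same section sets two-sided significance at 0.05, names the Satterthwaite t-test for comparing T-cell and dendritic-cell profiles with the controls, and calls the secondary analyses exploratory. Appendix F describes the comparison as one between the whole treated population and the controls. Section 3.1 restricts the controls to the correlative studies.

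**The concern.** A rate, a period and a target are given for the same group, and any two of them fix the third. Here they conflict, and the total of 64 is drawn from the target without regard to the other two.

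The correlative comparison is the only use the plan makes of the controls, so their number should follow from the plan. If the rate and period hold, neither power statement in Section 12.5 describes the sample that will exist. If the target holds and the rate is right, control accrual runs well past the end of treatment-arm accrual, and the later controls are no longer concurrent. The protocol addresses neither case. Nothing in it extends control accrual beyond the treatment arm or names a second source of controls.

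**Working it through.** **Inputs.** From Section 3.3: 2 treated patients per month, 44 treated, 24 months, 0.5 controls per month, 20 controls, total 64. From Section 12.5: two-sided 0.05, Satterthwaite t-test, effect sizes 1.0 and 1.1. The 24 months is read as the accrual period, because it is derived from the accrual rate.

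**Step 1: reproduce the stated power.** The pooled two-sample t-test power comes from the noncentral t distribution with n1 + n2 − 2 degrees of freedom and noncentrality d / √(1/n1 + 1/n2).

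- 20 vs 20, d = 1.0: noncentrality 1.0 / √(0.05 + 0.05) = 3.16, power 86.9% (stated 87%).
- 15 vs 15, d = 1.1: noncentrality 1.1 / √(2/15) = 3.01, power 82.8% (stated 83%).

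Both figures reproduce. Simulating the Satterthwaite test with equal variances gives 86.8% and about 82.8%, so the choice of test hardly matters when the groups are equal in size.

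**Step 2: accrual.**

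- Controls in 24 months: 0.5 × 24 = 12.
- Treatment accrual at exactly 2 per month: 44 / 2 = 22 months, hence 0.5 × 22 = 11 controls.
- Total: 44 + 12 = 56 (or 44 + 11 = 55), against 64.
- Time to reach 20 controls: 20 / 0.5 = 40 months, which is 40 − 24 = 16 months beyond the treatment arm.
- Rate needed for 20 controls: 20 / 24 = 0.83 per month (20 / 22 = 0.91 over 22 months).

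**Step 3: power with 12 controls** (two-sided 0.05, equal variances; Satterthwaite figures by simulation).

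| Treated vs controls | Effect size | Pooled t | Satterthwaite |
|---|---|---|---|
| 20 vs 12 | 1.0 | 75.5% | about 75% |
| 38 vs 12 | 1.0 | 84.1% | about 81% |
| 44 vs 12 | 1.0 | 85.4% | about 82.5% |
| 44 vs 11 | 1.0 | 83.0% | about 79% |
| 15 vs 12 | 1.1 | 77.9% | about 77.5% |
| 44 vs 12 | 1.1 | 91.3% | about 89% |

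With unequal groups the two tests separate. For 44 vs 12 the planned test loses about 3 points relative to the pooled test, so the Satterthwaite column is the one to quote.

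**The case against.** Four points can be made for the plan.

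First, 20 is the stated intention in both Section 3.3 and Appendix F, whereas 0.5 per month is only a forecast. If the target governs, the rate or the period is the wrong input, and 20 controls, 64 subjects and 87% all stand. This is right as far as it goes. A reader might infer that the trial will end with 12 controls, but the documents do not establish that. They establish only that the three figures cannot all hold.

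Second, the power statements are conditional on the group sizes they name, and both reproduce. This stands in full: there is no calculation error in Section 12.5. What remains is that 12 controls satisfy neither condition.

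Third, Appendix F compares all treated patients with the controls, which recovers much of the loss. At effect size 1.0, 44 vs 12 falls only about 4.5 points short of 87%, and at effect size 1.1 it exceeds the stated 83%. This is also correct, and it makes the 20 vs 12 figure the unfavourable case. But Section 12.5 gives no power for that comparison, and it requires usable samples from all 44 patients when some sampling runs to day 365.

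Fourth, the analyses are exploratory. This limits the importance of the point without resolving the inconsistency.

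**Conclusion.** The inconsistency in Section 3.3 is real: 12 controls (11 over 22 months) from the stated rate and period against a target of 20, and 56 subjects against 64. The gap of 8 in 20 is too large to be rounding.

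Its consequence for power depends on how many treated patients enter the comparison. At effect size 1.0 with the planned test, power is about 75% with 20 treated, about 81% with 38 and about 82.5% with all 44, against 87% for 20 vs 20. At effect size 1.1 it is about 77.5% for 15 vs 12 and 89% for 44 vs 12, against 83% for 15 vs 15. These figures assume equal variances, normally distributed measurements and complete samples.

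Two stronger readings are not supported. One is that every correlative analysis loses the stated power. The regulatory T-cell profiles are to be analysed by generalized estimating equations, which the two power statements do not cover, and the biomarker panel's stated aim is to predict acute GVHD. The other is that the trial's main conclusion is weakened. The Simon two-stage design, the primary estimate and the toxicity boundary make no use of the controls.

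**What to change.** Reconcile the control rate, accrual period and control number in Section 3.3, then bring Section 12.5 and Appendix F into line. Any one of these would do:

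1. Keep the rate and period. State 12 controls and 56 subjects, and give Satterthwaite power for the comparison Appendix F describes: about 82.5% at effect size 1.0 if all 44 treated patients give usable samples, with about 81% for 38 as a more cautious figure. The pooled-test value of 85.4% should not be used, because it is not the planned test.
2. Keep 20 controls and 64 subjects, and correct the rate to about 0.83 per month, with a reason to expect it.
3. Keep 20 controls at 0.5 per month. State a 40-month control period and acknowledge that controls from roughly the last 16 months have no treated patients accrued alongside them.

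Under any option, Section 12.5 should say how many treated patients enter the comparison. The first option costs wording and a slightly lower stated power. The second needs faster control recruitment, and the third a longer timeline. The primary analysis does not change.
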